The mechanism by which multiple patient records open simultaneously can lead to a wrongpatient error may be related to the ease with which users can toggle between patient records and the similar looking computer screens. The magnitude of this risk needs to be established to help IT leadership decide on how to safely implement CPOE systems. There have been no studies that have evaluated whether multiple records open increase the risk of wrong-patient errors, by how much, and if any increase is dependent on the number of records open (i.e., is four records open simultaneously more dangerous than three? Is three worse than two?). Our research is an important first step in quantifying this risk.

Practice of allowing multiple records opens at once. Investigators on this protocol conducted a national survey of Chief Medical Informatics Officers (CMIOs) via the American Medical Informatics Association listserv and the Association of Medical Directors of Information Systems listserv in March 2014. The survey assessed the practice of allowing multiple records open at once, as well as CMIOs' experiences and perceptions of the risks and gains in efficiencies of having multiple records open. There was a wide range of configuration of this feature across facilities. Of 167 facilities with CPOE systems capable of simultaneously displaying multiple patient records at once, 44.3% allowed three or more records open (unrestricted environment), and 38.3% limited the system to only one record open at a time (restricted environment). It is interesting to note that a number of respondents changed their settings some time after their initial configuration: three hospitals decreased the number of records allowed open at once; two hospitals increased the number of records allowed open at once; and one hospital went from allowing four records open at once down to one, and then back up to two. Table 1 provides some comments from CMIOs explaining why they chose to establish an unrestricted environment or restricted environment, and why some hospitals decided to switch configurations after the initial instillation. The results of this survey demonstrate that IT leadership is lacking objective data to guide their decision on how many patient records allowed open at once in EHRs.

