Provider-level covariates: type of ordering provider (attending, resident, physician assistant, nurse practitioner, pharmacist, or other), and total number of orders placed during the study period (a measure of the frequency with which the provider uses the system).

Patient-level covariates: age, race, ethnicity, sex, unit, and date and time of admission.

Order-session level covariates: location of the order session (emergency department, medicalsurgical unit, intensive care unit, labor and delivery, pediatrics, other specialty units).

Order level covariates: type of order (medication, imaging, nursing order, procedure, other), date and time of order, date and time of retraction, and number of patient records open at the time the order was placed.

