## FINAL STATISTICAL ANALYSIS PLAN

**Descriptive Analysis**. We will use descriptive analysis to examine provider-level, patient-level, order session-level, and order-level covariates for the orders placed in the restricted versus unrestricted mode. Descriptive statistics will be reported as mean and standard deviation for continuous variables, and as count and percentages for categories.

**Orders versus Order Sessions.** If a provider begins placing orders in the wrong patient's record, there is the possibility that several such orders will be placed and then retracted together. Therefore, individual orders do not represent independent opportunities for errors to occur. Orders are clustered within order sessions, defined as a series of orders placed consecutively by a single provider for a single patient that begins with opening that patient's order file and terminates when an order is placed on another patient or after 60 minutes, whichever comes first. Thus the order session, rather than each order, represents an independent opportunity for a wrong-patient error to occur.

**Primary Outcome.** The primary outcome measure, the Wrong-Patient RAR measure, is an electronic query run retrospectively against every order placed during the study period to identify instances in which one or more orders placed for a patient were retracted (cancelled) by the same provider within 10 minutes, and then reordered by the same provider for a different patient within the next 10 minutes (RAR events). The primary outcome is wrong-patient order sessions, defined as order sessions that include a wrong-patient RAR event identified by the Wrong-Patient RAR measure.

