**Primary Analysis (Aim 1)**. The primary analysis of the randomized trial is intention-to-treat, with each provider generating a cluster of order sessions. Hence, the order session will be used as the unit of analysis. The primary outcome variable is dichotomous, indicating whether or not each order session contains a wrong-patient RAR event. To determine the effect of trial arm on wrong-patient orders, we will construct a random effects logistic regression model with wrong-patient order sessions as the outcome, and randomization arm as the independent variable, using provider as a random intercept to account for clusters of order sessions within providers. We will estimate the effect of the restricted mode versus the unrestricted mode on the rate of RAR events using the odds ratio and its 95% confidence interval (CI), and will test the null hypothesis using the Wald test with a two-tailed significance level of 0.05. The primary outcome is reported as the number of wrong-patient order sessions per 100,000 order sessions.

**Subgroup Analysis (Aim 2).** Additional analyses of the effect of the restricted mode versus the unrestricted mode in specified clinical locations will be carried out by including indicators for the locations and location-study arm interaction terms in the model. For subgroup analyses, we will compare the rate of RAR events in emergency department, outpatient, and inpatient settings, and more specifically in inpatient units, including medical/surgical, critical care, pediatrics, and obstetrics units. We will construct similar mixed-effects logistic regression models for each predefined subgroup, with a separate model including an interaction term to test the significance of treatment effects across subgroups, using the Wald test for significance.

**As-Treated Analysis**. Because of administrative errors, some providers were not assigned to the trial arm to which they were randomized. Therefore, we will repeat all assessments in as-treated analyses (ie, according to treatment received) such that each order or order session was characterized by the provider's configuration at the time the orders were placed.

For orders placed in the unrestricted mode, we will examine the rate of RAR events and the percentage of orders placed when one, two, three, or four records were open at the time of ordering,

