overall and stratified by clinical setting. For these analyses the order will be used as the unit of analysis (rather than the order session), because a provider may open or close patient records while placing a series of orders during a single order session. We will report the number of RAR events per 100,000 orders along with 95% binomial confidence intervals, as well as the percentage of all orders placed under those conditions. These results will be presented for the unrestricted arm overall, and disaggregated by clinical location.

**Sample Size**. For pragmatic reasons, sample size is not determined by the investigators but will represent the data that is available during the study period. Moreover, as noted, orders do not represent independent events, but are clustered within order sessions that, in turn, are clustered within providers. The magnitude of the effects at these levels are not currently known. Based on prior experience in this setting, in 1 year of data collection we expected to obtain approximately 9,000,000 orders in 2,400,000 order sessions, placed by 3,200 distinct providers for 440,000 distinct patients. We assumed 100 wrong-patient order sessions per 100,000 order sessions in the Unrestricted arm, and an intra-provider correlation of 0.01. With accrual of approximately 1,600 providers in each randomization arm, and a trial duration yielding an average of approximately 1,300 order sessions per provider with a coefficient of variation of 1.2, the trial would have >99% power to detect an odds ratio of 0.5 (or lower), 96% power to detect an odds ratio of 0.7.

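### The records-open table uses binomial intervals that ignore the clustering the plan declares, and has no within-provider comparison to separate provider differences from the number of records open

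*Combined protocol and SAP*

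**What the plan says.** The protocol's Background and Significance asks "is four records open simultaneously more dangerous than three? Is three worse than two", and calls the research a first step in quantifying this risk. Randomization assigns only the maximum allowed, one record or four. It does not assign the number actually open when an order is placed.

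The one analysis that addresses the question is at the end of the SAP's As-Treated Analysis. There the plan says "we will examine the rate of RAR events and the percentage of orders placed when one, two, three, or four records were open", and presents the results "overall and stratified by clinical setting". On the unit it says "For these analyses the order will be used as the unit of analysis (rather than the order session", because records may be opened or closed during a session. On precision it says "We will report the number of RAR events per 100,000 orders along with 95% binomial confidence intervals". No model, provider term or covariate adjustment is specified for this analysis.

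Elsewhere the SAP is explicit about dependence. Under Orders versus Order Sessions it says that "individual orders do not represent independent opportunities for errors to occur", and Sample Size repeats that orders cluster within sessions, and sessions within providers. The primary model respects this by "using provider as a random intercept to account for clusters of order sessions within providers". Among the order-level covariates, the protocol lists "date and time of order, date and time of retraction, and number of patient records open at the time the order was placed".

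**The concern.** The table is the plan's only information on the two-versus-three-versus-four question, so readers are likely to compare the four rates and their intervals.

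- **Precision.** A binomial interval is valid only if orders are independent. The plan says that they are not, so differences between rows will look better established than they are.
- **Comparability.** The rows are formed by provider behaviour. If providers who often work with several records open also have higher or lower error rates for other reasons, the row-to-row ratio mixes that with any effect of the open records. Stratifying by setting removes differences between settings, but not between providers in the same setting. The log holds repeated orders from the same providers, so a within-provider comparison is possible wherever a provider's number of open records varies, but none is planned.

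A smaller point is the numerator. A RAR event can contain one or more orders, yet the rate is described as events per 100,000 orders. The text does not say whether each affected order is counted.

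**Working it through.** The plan gives no power, precision or expected result for this analysis, so there is no stated figure to reproduce.

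**Inputs from the SAP, Sample Size:** 9,000,000 orders, 2,400,000 order sessions, 3,200 providers, 100 wrong-patient sessions per 100,000 in the unrestricted arm, intra-provider correlation (ICC) 0.01 with no scale stated, and coefficient of variation (CV) of sessions per provider 1.2. Rates by provider type are in the protocol's Inclusion and Exclusion Criteria.

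**1. Interval width**
- Orders per session: 9,000,000 / 2,400,000 = 3.75.
- If RAR orders are counted, the standard error is understated by √(1 + (3.75 − 1) × r), where r is the within-session correlation of the RAR flag. The documents do not give r.
- r = 0.3: √1.825 = 1.35. r = 0.5: √2.375 = 1.54. r = 1: √3.75 = 1.94.
- This treats sessions as equal in size and lying wholly within one row. Provider clustering comes on top. If whole events were counted instead, this multiplier would not apply, but provider clustering would.

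**2. Between-provider spread implied by ICC 0.01**
- Proportion scale: variance = 0.01 × 0.001 × 0.999 = 9.99 × 10⁻⁶, so the CV of provider rates is 0.00316 / 0.001 = 3.16. The matching lognormal SD is √ln(1 + 3.16²) = 1.55.
- Latent logistic scale: variance = (π²/3) × 0.01/0.99 = 0.0332, so SD = 0.18.

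**3. Crude ratio with no true effect, two or more records open versus one**

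Provider rates are lognormal with SD s. Each provider's share of orders with two or more open is logit-normal with mean 0.33 and logit SD τ, and has correlation ρ with the log rate. The mean share, ρ and τ are assumptions. Weighting by the error rate shifts the mean logit share by ρ·s·τ. The crude ratio is therefore the odds of the mean share after the shift divided by the odds before it.

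Simulated results at τ = 1.0:

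| ρ | s = 1.55 (proportion scale) | s = 0.5 (intermediate) | s = 0.18 (latent scale) |
|---|---|---|---|
| 0.2 | 1.30 | 1.09 | 1.03 |
| 0.3 | 1.48 | 1.13 | 1.05 |

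Numerical evaluation of the formula agrees within 0.01. At ρ = 0 every entry is 1.00. At ρ = 0.1 the row is 1.14, 1.04, 1.02. τ matters too: at ρ = 0.2 and s = 1.55, the ratio is 1.16 with τ = 0.5.

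**4. Does a within-provider comparison remove this?**

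A separate simulation used 1,600 providers, a mean of 750 sessions (2,400,000 / 3,200) with CV 1.2, 3.75 orders per session, 58 RAR orders per 100,000 and no effect of records open. The log-rate SD was 0.2, 0.5 or 1.0. For ρ of 0.3 to 0.6, the crude four-versus-one ratio was 1.07–1.15, 1.18–1.41 and 1.42–2.01 respectively. The provider-stratified Mantel-Haenszel ratio stayed at 0.99–1.01 throughout.

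**5. Evidence of provider differences in the documents**

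Prior rates run from 33 (nurses) to 74 (nurse practitioners and physician assistants) per 100,000 orders. Provider type alone could therefore shift a crude ratio by at most 74/33 = 2.24, and only if each row held a single type.

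**The case against.** The strongest reply is that the table is only descriptive. It lies outside Aims 1 and 2, carries no test, ratio or causal statement, and is already split by setting. This stands, and it limits the weight of the point. It does not rescue the intervals, because a descriptive interval should still reflect the dependence the plan describes.

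Second, the bias figures rest on quantities that are not in the documents. This also stands. Nothing shows that error-prone providers open more records, or fewer, and the result depends on τ and on the ICC scale. Nor do the plan's power figures favour the large-bias reading. With ICC 0.01 on the proportion scale, the design effect is 1 + (2.44 × 1,300 − 1) × 0.01 = 32.71. That leaves 1,600 × 1,300 / 32.71 ≈ 63,600 effective sessions per arm and about 45% power at an odds ratio of 0.7, against the stated 96%. The latent scale gives about 100%.

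Third, the numerator may be only loose wording, since the order is the stated unit and the prior rates are orders over orders. That is a fair reading. A reader might infer that the mismatch distorts the gradient. The documents do not support this: a constant number of orders per event cancels between rows, and nothing shows that it varies with records open.

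Fourth, a within-provider model cannot remove confounding that changes over time, such as workload, and its ordinary model-based intervals would still ignore dependence within sessions. Both are correct, and the fix must allow for them.

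**Conclusion.** The point holds in a limited form. The binomial intervals conflict with the plan's own account of clustering. If RAR orders are counted, they are too narrow by about 1.35 to 1.94 for an assumed within-session correlation of 0.3 to 1, before provider clustering.

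The crude rates can also mix provider differences within a setting with the number of records open. With no true effect, ρ of 0.2 to 0.3 and τ of 1.0, the crude ratio is about 1.03 to 1.05 if the ICC is on the latent scale and 1.30 to 1.48 if it is on the proportion scale. It is 1.00 if ρ is zero, and a negative ρ would hide a real gradient.

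A reader might go further and infer that the table will show a false dose-response, or that the trial's main result is compromised. The documents support neither. They do not establish the sign or size of ρ, and the randomised comparison of the two modes does not use this table.

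**What to change.** 1. Keep the crude table, overall and by setting, and label it observational.
2. Replace the binomial intervals with provider-clustered ones, from a provider-level bootstrap or a cluster-robust variance. Sessions nest within providers, so these also cover within-session dependence.
3. State that the numerator is orders belonging to a RAR event, to match the order denominator.
4. Prespecify a supporting within-provider analysis of orders in the unrestricted mode. This would be a provider-conditional logistic model, or one with records open centred on the provider's mean. Enter records open as 1 (reference), 2, 3 and 4, adjust for location, order type and time of day, and use provider-clustered intervals here too.

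The cost is one more model on variables already planned for capture. Providers with no variation in records open, or with no RAR order, add nothing to the conditional estimate. Confounding that varies within a provider over time, such as workload, remains, so the result should carry the same observational label.

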#### **BACKGROUND AND SIGNIFICANCE**

**Frequency of wrong-patient orders.** At least 70,000 U.S. physicians use computerized provider order entry (CPOE) to place orders. Although CPOE is associated with a reduction in medical errors, when orders are placed electronically certain types of errors, including placing orders on the wrong patient, may occur more frequently.

The danger of wrong-patient electronic orders was highlighted by one hospital's report that after implementing CPOE, medications were prescribed for the wrong patient several times per month. In 2003, the United States Pharmacopeia analyzed 7,029 voluntarily reported medication errors over a 7-month period and found a mean of 9 wrong-patient orders at each of 120 participating institutions using CPOE. This report likely under-estimated the extent of wrong-patient electronic orders, as voluntary reporting is known to be an unreliable method for identifying errors. [name], the Principal Investigator of this proposal, developed an automated surveillance tool, the Wrong-Patient Retract-and Reorder measure, that identified 5,246 orders placed on the wrong patient in one year at a single academic medical center, with a rate of 58 wrong-patient orders per 100,000 orders. In that year, 1 in 6 providers placed an order on the wrong-patient, and 1 in 37 hospitalized patients had an order placed for them in error. This was the first study using automated surveillance to identify wrong-patient orders, and it demonstrated the prevalence of wrong-patient orders to be significantly higher than previously thought.

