# Data Capture

The data required to define orders, orders sessions, and the number of open patient records, patient and provider characteristics, and RAR events is automatically captured by the Epic EHR system. Investigators will collaborate with information technology personnel at the study sites and with Epic throughout the implementation phase of the study to develop the methodology for extracting the required data. At the end of the data collection period, data for all orders placed by study providers during the study period will be extracted, de-identified, encrypted, and transmitted electronically to the investigators for analysis. Preset batch orders (eg, for vaccines) will be excluded from the analysis, as these orders are not under the control of individual providers. These data sets will provide all of the information needed to carry out the analyses.

To examine the rate of wrong-patient orders and proportion of orders placed when one, two, three, or four records were open, an electronic log will be developed and programmed into the Epic system to record the number of records open at the time each order was placed.

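### The records-open table pairs order-level rates with binomial intervals although the SAP says orders are clustered; the variance is understated by an amount the documents do not fix

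*Combined protocol and SAP*

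**What the plan says.** The As-Treated Analysis section of the SAP plans RAR rates by number of records open in the unrestricted mode, overall and by clinical setting. It takes the order, not the session, as the unit because "a provider may open or close patient records while placing a series of orders during a single order session". On precision it says: "We will report the number of RAR events per 100,000 orders along with 95% binomial confidence intervals". It does not say which binomial interval (Wald, Wilson, exact) is meant.

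Two other SAP sections describe the dependence between orders. Orders versus Order Sessions says that "individual orders do not represent independent opportunities for errors to occur". Sample Size says that "orders do not represent independent events, but are clustered within order sessions that, in turn, are clustered within providers". The Primary Analysis deals with the provider level by "using provider as a random intercept to account for clusters of order sessions within providers". Nothing comparable is written for the records-open table.

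On counting, the SAP defines RAR events as "instances in which one or more orders placed for a patient were retracted (cancelled) by the same provider within 10 minutes" and then reordered for a different patient. Data Capture describes the same table with the words "To examine the rate of wrong-patient orders and proportion of orders placed when one, two, three, or four records were open", and Background reports the prior study "with a rate of 58 wrong-patient orders per 100,000 orders". The covariate list in Methods makes the number of open records an order-level variable, and Data Capture has it logged for every order.

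**The concern.** The reason given for leaving the session is sound, but it justifies the unit and not a variance that treats orders as independent. Wrong orders may be placed and retracted in batches, and providers may differ in their error rates. Either makes the true sampling variance larger than the binomial one.

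Background asks whether four open records are more dangerous than three, and three than two. This table is the only planned analysis of that question, and its intervals are the only uncertainty measure attached to it. Readers will judge the four rates, and the settings, by those intervals.

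**Working it through.** The SAP gives no precision figure for this table, so there is none to reproduce. The one stated result that uses the clustering inputs is 96% power at an odds ratio of 0.7. It does not reveal the scale of the correlation. With 1,300 sessions per provider, a normal approximation gives about 80% on the proportion scale (equal clusters) and about 100% on the latent scale. The power method is not stated, and this point does not depend on it.

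**Inputs (SAP, Sample Size, unless noted).** 9,000,000 orders, 2,400,000 sessions and 3,200 providers, so 3.75 orders per session and m = 750 sessions per provider; 1,600 providers per arm; 100 wrong-patient sessions per 100,000; intra-provider correlation 0.01, scale not stated; coefficient of variation of cluster size 1.2. Prior-study counts (Preliminary Studies): 6,885 retracted-and-reordered orders, or 5,246 after correction for positive predictive value. Stratum shares are my assumption.

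**A. Each event counts once (provider clustering only).** Width factor = sqrt(1 + m × (1 + 1.2²) × share × 0.001 × CV²), where CV is the between-provider coefficient of variation of the event rate.

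- Latent scale: variance = (0.01/0.99) × π²/3 = 0.0332; CV² = exp(0.0332) − 1 = 0.0338.
- Proportion scale: CV² = 0.01 × 0.999/0.001 = 9.99, so the provider SD is 3.16 times the mean rate.

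| Share of orders | Latent | Proportion | Approx. coverage, proportion scale |
|---|---|---|---|
| 10% | 1.003 | 1.68 | 76% |
| 25% | 1.008 | 2.36 | 59% |
| 100% | 1.030 | 4.39 | 35% |

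With the SAP's stated 1,300 sessions per provider instead of 750, the 10% and 25% rows become 1.005 and 1.013 (latent) and 2.04 and 2.99 (proportion).

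The interval type also matters. The unrestricted arm would have about 1,600 × 750 × 0.001 = 1,200 events, so 60, 120 and 300 events at shares of 5%, 10% and 25%. With latent-scale overdispersion, exact binomial intervals cover about 95% to 96% at these shares.

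**B. Each wrong order counts (batching only; provider clustering comes on top).** Planned affected sessions: 2,400,000 × 0.001 = 2,400. Wrong orders per affected session, b: 5,246/2,400 = 2.19 or 6,885/2,400 = 2.87.

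- Batch stays in one stratum, equal batches: sqrt(b) = 1.48 to 1.69.
- Batch stays in one stratum, batch size 1 + Poisson(b − 1): sqrt(E[b²]/E[b]) = 1.65 to 1.88.
- Batch scatters over strata, with share q: sqrt(1 − q + q × E[b²]/E[b]) = 1.20 to 1.28 at q = 25%, and 1.08 to 1.12 at q = 10%.

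Example: 58 per 100,000 in an assumed stratum of 450,000 orders has a binomial half-width of 7.0 per 100,000. Multiplied by 1.48 to 1.69, this becomes 10.4 to 11.9.

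**C. Level of the rate.** Events once: 2,400/9,000,000 = 26.7 per 100,000 orders. Orders counted: 58 (corrected) or 6,885/9,000,000 = 76.5 (uncorrected). This contrast rests on the same ratio as b, so it is not separate evidence.

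**D. Differences between strata.** In a simulation with four strata of equal expected share and events counted once, the factor for a difference was 0.99 to 1.04 on the latent scale. On the proportion scale it ran from 1.0 when all providers share one records-open mix to 3.0 when mixes vary strongly.

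**The case against.** The best case against acting is that the effect may be negligible and the table has little weight. Much of that stands. On reading A with a latent-scale correlation the correction is 3% or less. The table has no planned test, lies outside Aims 1 and 2, and feeds no decision rule. Providers choose how many records to open, so the comparison is not randomised, and clustered intervals would not make it causal.

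Three stronger readings are tempting, and the documents do not support them.

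- A reader might infer that every interval is too narrow as soon as there is any positive clustering. The variance is understated, but the interval type is not named, and exact intervals are conservative enough to hold 95% in the mild case.
- A reader might infer that neither the counting rule nor the stratum rule can be found. In fact the order is the unit and the number of open records is logged for each order. Together these point to a yes/no outcome per order, placed in that order's own stratum. What remains unclear is the phrase RAR events, since one event may cover several orders.
- A reader might quote factors of 4 or more. Those need one stratum to hold all orders and a provider SD about three times the mean.

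The objection does not remove the inconsistency itself. The SAP describes the size of the clustering effects as unknown, so it cannot presume them negligible. The per-order reading that helps with the stratum rule is also the one under which batching matters.

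**Conclusion.** The concern holds in a limited form. The planned variance for the records-open table assumes an independence that the SAP denies, so it is understated; confidence in that direction is high. Confidence in the size is low. It runs from negligible (1.00 to 1.03 times in width: events once, latent-scale 0.01, m = 750) through about 1.5 to 1.9 times (orders counted, batches kept in one stratum) to about 1.7 to 2.4 times at shares of 10% to 25% (events once, proportion scale, m = 750).

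The middle range depends on 2.2 to 2.9 orders per affected session. That figure divides prior-study order counts by a planning figure that applies the assumed unrestricted-arm rate to both arms, and its lower end sets a corrected numerator against an uncorrected denominator. The last range is an upper case because of the provider variation it implies.

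This is a low-priority correction to a descriptive table. The primary and subgroup models are not touched.

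**What to change.** Keep the order as the unit, with each order in the stratum logged for it. Replace the binomial intervals with provider-clustered ones, by a provider-level bootstrap or a provider-clustered robust variance, both overall and by clinical setting. Clustering at the provider level also covers sessions nested within providers. Show event counts beside sparse cells. If strata are compared, take the contrast and its interval from the same method and do not judge by overlap of intervals. As a clarification of wording, state whether a multi-order RAR event counts once or once per order; if once, also say which stratum it takes when the number of open records changes within it.

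The cost is about two sentences in the SAP and a little programming, with no new data. Intervals will be somewhat wider, and clustered or bootstrap intervals are themselves unstable in sparse setting-by-records cells, which is why the event counts should be shown.
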